## **2.0 OVERVIEW AND STUDY DESIGN**

This study is to look at the efficacy of reducing the dose of craniospinal radiation to limit adverse effects, while adding concurrent carboplatin administration during radiation with weekly vincristine for metastatic medulloblastomas and high-risk supratentorial PNETs and metastatic PNETs. Pilot data from Children's Oncology Group (COG) study 99701 show excellent results with daily carboplatin infusion during radiation for high risk central nervous system tumors (Jakacki et al, 2006). This study had an 89% 3 year event free survival for classical histology metastatic medulloblastoma. Anaplastic medulloblastomas did poorly and will be excluded from the current study.

Although the COG 99701 study had excellent event free survival, 36 Gy radiation dose to the craniospinal axis was used. This dosage is known to be associated with extremely poor quality of life as an adult (Ribi et al, 2005, Packer et al, 1994). The improvement of survival of COG 99701 over all prior studies appears to be due to the addition of carboplatin during radiation. The current study proposes to see if the addition of carboplatin during radiation allows for lowering the craniospinal radiation dose to 23.4 Gy, a dose which is known to be associated with a satisfactory quality of life for adult survivors (Ribi et al, 2005, Packer et al, 1994).

In order to assess efficacy we would accept equivalency in terms of 90% event free survival from progression at 3 years. We will re-assess the therapy after every 10 patients completes the study. One

failure within every ten patients would close the study. Following concurrent carboplatin, vincristine, and craniospinal radiation at 24 Gy, patients will receive the current standard adjuvant chemotherapy.

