### **13.33 Analysis of Efficacy**

If there are 1 or fewer deaths from tumor progression, within 10 patients, with 3 years median follow up, then a presumption can be made that the reduction in radiation dose has not led to a decline in efficacy. The information would then be supplied to the national group (Children's Oncology Group) as a potential next national Phase III, randomized study.

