## **13.4 Interim Monitoring**

### **13.41 Interim Monitoring of Treatment Efficacy**

Because of the short duration of this study, therapeutic efficacy as measured by either EFS or survival, will not be subject to interim monitoring. The first formal analysis of this study will occur when median follow-up is approximately 18 months. The formal early monitoring of dose limiting toxicities and any toxic deaths will provide early warning of significant safety problems.

Because we expect a survival of approximately 90%, if there is one failure in ten patients, we will accept that as equivalent. If there are 2 deaths from tumor progression within the first 10 patients, the study will be closed. All patients will subsequently be monitored. If there are no further deaths and the number of patients is still less than 10, the study will be re-opened to accumulate a total of 10 patients. The expectation is that there will be no toxic deaths. Any toxic deaths will result in the suspension of the study, investigation into the cause of death, and discussion with the IRB.

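### One failure in ten closes the study under section 2.0 but is acceptable under 13.41 and 13.33, and the 90% event-free target is judged on tumour deaths alone

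*Protocol*

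**What the plan says.** Four places in the protocol bear on the efficacy decision.

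- **Section 2.0** sets the target: "we would accept equivalency in terms of 90% event free survival from progression at 3 years". It continues: "We will re-assess the therapy after every 10 patients completes the study". It then says that one "failure within every ten patients would close the study" (the word *One* stands just before a page break, but the sentence is complete). The reference result is also given there: "This study had an 89% 3 year event free survival for classical histology metastatic medulloblastoma".
- **Section 13.31** defines event-free survival (EFS) as time to progression or recurrence, death from any cause, or a second malignancy. Section 13.0 makes estimating EFS part of the primary objective.
- **Section 13.33** gives the efficacy criterion: "If there are 1 or fewer deaths from tumor progression, within 10 patients", at 3 years median follow-up, then "a presumption can be made that the reduction in radiation dose has not led to a decline in efficacy". The information then goes to the national group as a potential Phase III study.
- **Section 13.41** says "Because we expect a survival of approximately 90%, if there is one failure in ten patients, we will accept that as equivalent", and then: "If there are 2 deaths from tumor progression within the first 10 patients, the study will be closed". Toxic deaths are handled separately, by suspension and investigation.

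Sections 4.2 and 13.1 plan about 10 patients. *Failure* is not defined in 2.0 or 13.41.

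**The concern.** There are two faults.

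**Threshold.** One failure in ten closes the study under 2.0, is equivalent under 13.41, and supports the presumption of no decline under 13.33. Section 2.0 also disagrees with itself, because its target of 90% allows the one failure that its closure sentence does not.

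**Counted event.** The target in 2.0 concerns freedom from progression events. The criterion in 13.33 and the closure sentence in 13.41 count only deaths from tumour progression. A patient who has progressed but is alive fails the target and is counted by neither rule.

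At stake is the trial's main decision: whether a reduced craniospinal dose is reported as having cost no efficacy and is put forward for a randomised trial. With these texts, the choice of rule could be made after the result is known.

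**Working it through.** **The plan's own figure.** Expected failures at 90% among 10 patients: 10 × (1 − 0.90) = 1. This agrees with 13.41 and with the target in 2.0, and disagrees with the closure sentence in 2.0.

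**The rules side by side** (10 patients, the same event counted everywhere):

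| Failures in 10 | Section 2.0 | Section 13.41 | Section 13.33 |
|---|---|---|---|
| 0 | continue | continue | no decline presumed |
| 1 | close | equivalent | no decline presumed |
| 2 | close | close | not met |

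The sections conflict at exactly one failure.

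**How likely that is.** With X ~ Binomial(10, p): P(0) = (1 − p)^10, P(1) = 10p(1 − p)^9, P(≥2) = 1 − P(0) − P(1). The value p = 0.10 comes from the 90% target and p = 0.11 from the cited 89% 3-year EFS.

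| p | P(0) | P(exactly 1): conflict | P(≥1): 2.0 trigger | P(≥2): 13.41 trigger |
|---|---|---|---|---|
| 0.10 | 0.3487 | 0.3874 | 0.6513 | 0.2639 |
| 0.11 | 0.3118 | 0.3854 | 0.6882 | 0.3028 |

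These use 3-year failure rates. The closure rule in 13.41 has no time window, so an earlier look would trigger it less often. As an illustration, assume a constant hazard and 18 months of follow-up for every patient. Then p = 1 − 0.90^0.5 = 0.0513 gives P(≥2) = 0.0901, and p = 1 − 0.89^0.5 = 0.0566 gives P(≥2) = 0.1066.

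**Event mismatch, by example.** Take 10 patients with 1 tumour death and 3 living patients with progression. EFS events = 1 + 3 = 4, so 6/10 = 60% are event-free against a target of 90%. Tumour deaths = 1, so 13.33 is met and 13.41 does not close.

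**Event mismatch, by probability.** The protocol does not give the share q of EFS events that are tumour deaths by the time of analysis, so q is an assumption shown over a range. P(13.33 met) = P(at most 1 tumour death), with tumour deaths ~ Binomial(10, q(1 − EFS)):

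| True 3-year EFS | q = 1 | q = 0.75 | q = 0.5 |
|---|---|---|---|
| 90% | 0.736 | 0.830 | 0.914 |
| 80% | 0.376 | 0.544 | 0.736 |
| 70% | 0.149 | 0.305 | 0.544 |

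The column q = 1 is also the probability of at most one EFS event. At a true EFS of 70%, counting tumour deaths when half of the events are such deaths raises the chance of presuming no decline from 14.9% to 54.4%.

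**The case against.** - **Limited effect on accrual.** Section 2.0 re-assesses after ten patients complete and about ten are planned, so its trigger would stop little or no enrolment. This stands: the 65.1% and 68.8% should not be read as chances of cutting accrual short. The conflict over what the result means remains.
- **Only one overview sentence is out of line.** Sections 13.33 and 13.41 agree on event and limit, and the target in 2.0 also implies one in ten. This is true, and it makes the correction easy, but the protocol still states both rules. A statistical analysis plan could not make both true.
- **Section 13.33 does not claim to test the EFS target.** It offers a presumption, and EFS is estimated separately. Also, the EFS from progression in 2.0 may be narrower than the definition in 13.31, which adds any death and second malignancy. Both are fair readings. But 13.33 is headed as the analysis of efficacy and draws the efficacy conclusion, and a living patient with progression fails the target in 2.0 on either reading.
- **A closure rule may count deaths, and toxic deaths have their own route.** This is accepted. Toxic deaths lead to suspension and review. Living patients with progression have no such route.
- **Some figures are illustrative.** The 89% applies to classical metastatic medulloblastoma only, while section 4.1 also admits desmoplastic histology and PNET. The 18-month figures rest on a constant hazard and apply an EFS rate to tumour deaths. The 60% example is constructed and shows what is possible, not what is likely. None of them is needed for the contradiction, which is in the text.

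**Conclusion.** The concern holds. Section 2.0 contradicts 13.41, 13.33 and its own 90% target at exactly one failure in ten. If one event is counted throughout and patients fail independently, that result has a probability of 38.7% at a 10% failure rate and 38.5% at 11%. A trial performing exactly on target would meet the 2.0 closure condition about two times in three.

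The event mismatch also holds: the presumption of no decline can be made while the EFS target is clearly missed. How often depends on the share of events that are tumour deaths, which the protocol does not give. The practical weight falls on interpreting the result and passing it to the national group, and less on stopping enrolment.

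**What to change.** Amend the protocol text; this review does not say which rule should prevail.

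1. Reconcile 2.0 with 13.33 and 13.41 so that no result both closes the study and counts as no decline in efficacy.
2. Define *failure* in 2.0 and 13.41.
3. State for each rule whether it counts EFS events or deaths from tumour progression, and make the presumption in 13.33 consistent with the 90% EFS target in 2.0. A closure rule may count deaths if the text says so.
4. State when the closure rule in 13.41 is assessed, distinguish it from the final criterion in 13.33 at 3 years median follow-up, and align the re-assessment after every ten patients in 2.0 with the planned total of about ten.

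Two optional clarifications would help. One is to say that a study re-opened after two tumour deaths can no longer meet 13.33, though it still serves the EFS and intellectual-function aims in 13.0. The other is to explain how the statement in 13.41 that efficacy is not monitored at interim fits with its death-count closure rule.

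The cost is wording only: sample size, visits and data collection do not change. If 13.33 is tied to EFS events, it becomes harder to meet than with tumour deaths alone.

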## **4.2 Subject Enrollment**

Approximately 10 subjects will be enrolled locally at Children's Hospital Colorado. Eligible subjects will be offered participation in the study by their primary physician through the Neuro-Oncology Program at Children's Hospital Colorado. The subjects may be inpatients or outpatients.

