### 13.1 **Patient Accrual**

The Neuro-Oncology Program at Children's Hospital Colorado has seen an average of 5 patients per year with metastatic medulloblastoma, high risk PNET and metastatic PNET. We expect to enroll 10

patients. The current standard of care CCG 9961 was based on a pilot study of 10 patients (Goldwein et al, 1996).

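### Section 13.41 re-opens accrual after two tumour deaths without saying that the Section 13.33 criterion can then no longer be met, and states no purpose or observation period for the added patients

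*Protocol*

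**What the plan says.** Planned size is 10: Section 13.1 says "We expect to enroll 10" patients, and Section 4.2 says "Approximately 10 subjects will be enrolled locally".

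The success criterion is in Section 13.33: "If there are 1 or fewer deaths from tumor progression, within 10 patients, with 3 years median follow up". When that is met, the stated consequence is: "then a presumption can be made that the reduction in radiation dose has not led to a decline in efficacy". The result would then go to the national group as a candidate for a Phase III trial.

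Section 13.41 uses the same threshold: "Because we expect a survival of approximately 90%, if there is one failure in ten patients, we will accept that as equivalent". The closing rule follows: "If there are 2 deaths from tumor progression within the first 10 patients, the study will be closed". Patients are then to be monitored, for a period that is not given. The re-opening rule first requires that nobody else has died; on that condition, if "the number of patients is still less than 10, the study will be re-opened to accumulate a total of 10 patients". Accrual thus resumes to a cumulative target.

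Two other statements bear on this. Section 2.0 says that a single failure in ten closes the study. Section 13.41 itself opens by saying that event-free survival and survival will not be monitored at interim, and then gives a closing rule based on deaths.

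**The concern.** The closing rule and the success criterion fit together: two tumour deaths exceed the one that is accepted, so accrual stops. The re-opening sentence breaks that link. It resumes accrual on the ground that nobody else has died, yet the two deaths that caused closure remain in the count of 10.

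Patients enrolled after re-opening would receive the reduced craniospinal dose, as all patients do under Section 12.531, in a study that can no longer reach the one favourable efficacy conclusion that Section 13.33 defines. The protocol does not tell the investigator or the IRB that this is so. It does not say what the added patients are for, or how long the survivors must be observed before the condition of no further deaths counts as met. That last gap matters because Sections 2.0 and 13.33 judge efficacy on a 3-year horizon.

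**Working it through.** **Inputs.** Total N = 10 (Sections 4.2 and 13.1). Success: tumour deaths D ≤ 1 in 10 (Section 13.33). Closure: D = 2 (Section 13.41). Re-opening: fewer than 10 enrolled and no further deaths, up to a total of 10 (Section 13.41). Expected survival: about 90% (Section 13.41).

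**The plan's own figure.** Expected failures = 10 × (1 − 0.90) = 1, which agrees with the one failure in ten that Section 13.41 accepts. The protocol gives no alpha, power or margin here, so there is no sample-size formula to reproduce.

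**Is the re-opened cohort a fresh ten?** No. The condition is that the number enrolled is still below 10, and the target is a total of 10. Both count from the first patient.

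**Can Section 13.33 be met after re-opening?** Let k be the number enrolled at closure and X ≥ 0 the tumour deaths among all patients after that point. Then D = 2 + X ≥ 2, while success needs D ≤ 1. Hence P(D ≤ 1 | re-opened) = 0, even if every added patient survives.

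| Enrolled at closure, k | Patients added, 10 − k | Best result at 10 | P(Section 13.33 met) |
|---|---|---|---|
| 2 | 8 | 8/10 | 0 |
| 4 | 6 | 8/10 | 0 |
| 6 | 4 | 8/10 | 0 |
| 9 | 1 | 8/10 | 0 |

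The other values of k from 2 to 9 give the same zero. At k = 10 the study can close but not re-open.

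**How often could this arise?** It needs two tumour deaths before the tenth enrolment. Suppose each outcome is known before the next patient enrols. Real follow-up lags behind enrolment, so this gives an upper bound. With survival s,

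P(at least 2 deaths in 9) = 1 − s⁹ − 9(1 − s)s⁸.

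- s = 0.90 (the protocol's expectation): 1 − 0.3874 − 0.3874 = 0.225
- s = 0.80 (illustrative): 0.564
- s = 0.70 (illustrative): 0.804

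The extreme of closure with only two enrolled has probability 0.10² = 0.01 at 90% survival. For comparison, a full cohort of 10 meets Section 13.33 with probability 0.90¹⁰ + 10 × 0.10 × 0.90⁹ = 0.736 at 90% survival, and 0.376 at 80%.

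**Section 2.0 against Section 13.41.** At exactly one failure in ten, Section 2.0 closes the study and Section 13.41 accepts the result as equivalent. Both cannot govern.

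**The case against.** The strongest reply is that Section 13.33 is not the whole purpose. Section 13.0 states the primary objective as preliminary estimates of event-free survival and evidence of less intellectual decline. Section 13.31 lists event-free survival, overall survival and intellectual competence as efficacy endpoints. Added patients inform all three. If closure came at six patients, freedom from tumour death would be 4/6 = 67% (exact 95% interval about 22 to 96%). Four more patients, all surviving, would make it 8/10 = 80% (about 44 to 97%). These intervals ignore the fact that deaths triggered the closure, but the gain in information is real. Section 13.33 is also worded as a sufficient condition: it does not say that two deaths prove a decline or end the study's usefulness. Re-opening could be read as a pause after an early cluster of deaths, followed by completion of the planned cohort.

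This stands in part. A reader might infer that the whole efficacy answer is fixed and that added patients contribute nothing. The documents do not support that; only the Section 13.33 presumption, and the matching one-in-ten equivalence in Section 13.41, are out of reach. The reply does not remove the defect, because the protocol never gives estimation as the reason for re-opening.

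Two other readings also go too far. One is that a pause of any length satisfies the condition: Section 13.41 requires monitoring first and gives no duration, which is a gap and not a statement that any duration will do. The other is that re-opening encourages a favourable view of two deaths in ten: that is speculation, since Section 13.33 plainly withholds the presumption at two.

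**Conclusion.** The inconsistency is real but conditional, and I would rate it as should-fix. After re-opening, the Section 13.33 criterion cannot be met at any true survival. This follows from the text alone and needs no distributional assumption. Between 1 and 8 further patients could be enrolled in that state with no stated purpose and no stated observation period.

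The frequency does rest on assumptions: independent outcomes, the protocol's 90% taken as freedom from death due to tumour progression, and outcomes known before the next enrolment. On these, at most about 22.5% of studies would reach two tumour deaths among the first nine patients. Follow-up lag lowers the figure; true survival below 90% raises it. Prolonged accrual, which Section 13.2 reports, leaves more time for deaths before the tenth enrolment and so moves the real frequency closer to the bound.

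The finding does not establish that re-opening is without value, or which closing rule is correct.

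**What to change.** Reconcile the closing, re-opening and success rules across Sections 2.0, 13.33 and 13.41, including whether one or two failures in ten closes the study.

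If the re-opening provision is kept, add to Section 13.41:

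- that the Section 13.33 presumption is unavailable once two tumour deaths have occurred;
- the purpose of resumed accrual, for example estimation only, with IRB agreement;
- the observation period over which the absence of further deaths is judged.

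If no such purpose is intended, remove the provision. The choice belongs to the sponsor and the IRB.

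The cost is a short amendment: a sentence or two in Section 13.41 and an aligned sentence in Section 2.0. If the provision is removed, a study that stays closed may report fewer than 10 patients, with correspondingly less precise survival and intellectual-function estimates.

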### **13.5 Gender and Ethnic Origin**

There is no compelling evidence to suggest that outcome of treatment for brain tumors in children is dependent on gender or ethnicity. Hence, the study size will not be powered to detect differences in outcome in groups defined by ethnicity or gender. Therapeutic outcomes will nevertheless be compared among gender and ethnicity categories.

## **14.0 ADVERSE EVENT REPORTING REQUIREMENTS AND TOXICITY CRITERIA**

### **14.1 Purpose**

Adverse event data collection and reporting, which are required as part of every clinical trial, are done to ensure the safety of patients enrolled in the studies, as well as those who will enroll in future studies using similar agents. Adverse events are reported in a defined manner at scheduled and emergent times during a trial, based on occurrence and severity.

### **14.2 Reporting Requirements**

In this study a serious adverse event (SAE) includes death, life-threatening, hospitalization or prolongation of hospitalization, congenital anomaly/birth defects, and persistent and/or significant disability.

Any adverse event that is unexpected and related or possibly related to the study treatment or other research intervention will be reported. Any adverse event that is unrelated to the research intervention does not have to be reported to the COMIRB.

The principal investigator will, within 24 hours, or recognition of any grade 4, non-hematologic SAE that is likely due to radiation, vincristine, or carboplatin, contact the COMIRB.

Death due to disease will be reported if the death occurs within 30 days of the study treatment. All deaths that are possibly related to the study treatment that occur more than 30 days after the treatment will be reported immediately. All other deaths that are due to disease (and therefore expected) and unrelated to the treatment, will be reported at continuing review.

### **14.3 Toxicity Criteria**

Any patient experiencing a non-hematologic, irreversible grade 3 toxicity or grade 4 toxicity should not receive further Carboplatin. The site, measure and grade for all toxicities (Grade 3 and 4) will be according to the NCI Common Terminology Criteria v. 3.0 (CTCAE). The CTCAE provides descriptive terminology and a grading scale for each adverse event listed. A copy of the CTCAE can be downloaded from the Cancer Therapy Evaluation Program (CTEP) home page (<http://ctep.cancer.gov>)

## **Appendix 1: Neurological Exam Guidelines**

(Within normal limits)

**Head Tilt:** (Absent)

**Visual Acuity:** (Intact)

**EOMI:** (PERRLA)

**Cranial Nerves VII - XII:** (Intact)

**Extremities:** (Power, sensation, tone equal bilaterally)

**Gait:** (WNL)

**Dysmetria:** (No)

**Speech:** (Clear)

**Memory:** (Intact)

**Sensory:** (Normal)

## Appendix 2

### Karnofsky/Lansky Performance Scales

Karnofsky (Age at least 16 years)		Lansky (Age less than 16 years)	
Score	Description	Score	Description
100	Normal, no complaints, no evidence of disease	100	Fully active, normal.
90	Able to carry on normal activity, minor signs or symptoms of disease.	90	Minor restrictions in physically strenuous activity.
80	Normal activity with effort; some signs or symptoms of disease.	80	Active, but tires more quickly
70	Cares for self, unable to carry on normal activity or do active work.	70	Both greater restriction of and less time spent in play activity.
60	Required occasional assistance, but is able to care for most of his/her needs.	60	Up and around, but minimal active play; keeps busy with quieter activities.
50	Requires considerable assistance and frequent medical care.	50	Gets dressed, but lies around much of the day; no active play, able to participate in all quiet play and activities.
40	Disabled, requires special care and assistance.	40	Mostly in bed; participates in quiet activities.
30	Severely disabled, hospitalization indicated. Death not imminent.	30	In bed; needs assistance even for quiet play.
20	Very sick, hospitalization indicated. Death not imminent.	20	Often sleeping; play entirely limited to very passive activities.
10	Moribund, fatal processes progressing rapidly.	10	No play; does not get out of bed.

## Appendix 3

